## Randomization

All cases will be randomly allocated according to flip coin test into 2 groups each group will include 8 patients.

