# Patients and Methods

## Patient selection

this study will be conducted on 16 patients indicated for horizontal ridge augmentation in premolar and molar area. After approval from the ethical committee, the entire patients will be recruited from the outpatients' clinic of the Oral Medicine, Oral Diagnosis, and Periodontology Department Faculty of Dentistry, Minia University.

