## Ethical regulation and Informed consents

All patients will undergo a delayed implant placement and the complete treatment plan will be explained to all patients including detailed steps, risks, and expected results. Verbal and written informed consent will be obtained from all patients before the commencement of the study. All steps will be examined and approved by the appropriate ethics committee and have therefore been performed following the ethical standards laid down in the Declaration of Helsinki and the research ethics committee of the Faculty of Dentistry, Minia University.

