## Pre-surgical phase

- At the initial visit, each patient will receive a diagnostic work-up that included a full periodontal examination, standardized periapical radiographs and diagnostic study casts.
- Horizontal ridge width will be measured with a bone caliper to the nearest millimeter at the midridge crestal level and then 5 mm apically. Stent will be used for the standardization of the measurements.
- A preoperative cone-beam computed tomography (CBCT) will be performed for each patient who met the inclusion criteria before the surgery to determine bone height and width and to evaluate the underlying bone condition.
- These clinical and radiographic measurements will be repeated at reentry after 6 months of healing.

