### **Group A:**

: 8 patients indicated for lateral ridge augmentation in premolar-molar area (class I Seibert's classification) will be candidates to screw tent technique using single screw at crest position

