## **Surgical Phase**

- All patients will receive prophylactic antibiotic (1 gm. Amoxicillin-clavulanate, Augmentin ®, GlaxoSmithKline, UK) one hour preoperatively and then every twelve hours for four days and will be instructed to rinse with 0.12% Chlorhexidine (Orovex ®, MACRO, Egypt) for one minute prior to surgery and twice daily for 2 weeks postoperatively.
- All procedures will be performed under local anesthesia utilizing articaine hydrochloride 4% with 1:100000 epinephrine (Septanest®, Septodont, USA).
- Sulcular incisions around teeth with mesial and distal vertical releasing incisions. A full thickness flap will be reflected on the buccal, and a full thickness flap will be reflected on the lingual/palatal to expose the residual alveolar ridge.
- Multiple cortical perforations will be performed with a 1/2 round bur to increase angiogenesis and supply of growth factors in all defect areas.
- In group A: single titanium bone screw will be placed in a crestal position to aid in graft stability. In group B: double titanium bone screws will be placed, one at a crestal position and the other one will be placed 5mm apical to the first one.
- In both groups the defect will be filled with allograft, the graft will be extended at least 10 to 12 mm in the apicocoronal direction.
- The grafted site will be covered with Bovine pericardium membrane
- Tension-free primary flap closure will be achieved and sutured using a 5-0 Polypropylene suture.
- 6 months later at the reentry, the bone screws will be removed and dental implant will be placed at the augmented site.

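### A coin flip and an exact 8:8 split are both fixed, with no rule that links them and no concealment of upcoming assignments

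*Protocol*

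**What the plan says.** The Randomization section of the protocol consists of one sentence: "All cases will be randomly allocated according to flip coin test into 2 groups each group will include 8 patients". The total comes from Patient selection: "this study will be conducted on 16 patients indicated for horizontal ridge augmentation". The Group A and Group B sections each repeat the figure of 8, for example "8 patients indicated for lateral ridge augmentation in premolar-molar area". The sizes are therefore consistent (8 + 8 = 16), and they are fixed rather than approximate.

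The protocol gives no list, blocks, pairing, redraw rule or stopping rule. It does not say who flips the coin, when the flip takes place relative to enrolment, or how the next assignment is kept from those who recruit.

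Two other sections bear on timing without settling it:

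- Ethical regulation and Informed consents: "Verbal and written informed consent will be obtained from all patients before the commencement of the study".
- Pre-surgical phase, on the baseline CBCT: "will be performed for each patient who met the inclusion criteria before the surgery". This places the scan before surgery, not before allocation.

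**The concern.** A coin flipped independently for each patient does not fix the group sizes, so the sentence is incomplete: an unstated rule must turn flips into 8 and 8. Which rule it is matters, because some rules keep the sequence fully random and others make part of it known in advance. Overriding individual flips ad hoc to restore balance would not be random at all.

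Single versus double screw, the second aim, is the only randomised comparison in the trial. The surgeon necessarily sees the arm (Surgical Phase: "In group A: single titanium bone screw will be placed in a crestal position"). That is inherent in the comparison and no fault of the randomisation text, but it means the running totals can be known. If allocation is sequential and unconcealed, knowledge of the next assignment could influence which patient is enrolled, or when. With 8 per group each patient is 1/8 = 12.5% of a group mean, so steering even one or two patients could shift the comparison.

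**Working it through.** **Inputs.** 16 patients (Patient selection); 8 per group (Randomization, Group A, Group B); coin flip (Randomization). Assumption: the coin is fair and flips are independent, since the protocol says no more.

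**Does the stated mechanism give the stated sizes?** With X ~ Binomial(16, 0.5):

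- P(8:8) = C(16,8)/2^16 = 12870/65536 = 0.196, so P(not 8:8) = 0.804.
- P(10:6 or worse) = 0.454; P(11:5 or worse) = 0.210; P(12:4 or worse) = 0.077.

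The total of 16 is reproduced. The 8:8 split is not, unless a further rule is added.

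**What would different rules imply?** None of the rules below is in the protocol; they illustrate the range. An assignment is called determined when the running totals leave only one possible arm (or, for pairs, when the first of the pair is known).

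1. *Flip until one group has 8, then fill the other.* The first group fills at patient t with probability 2·C(t−1,7)/2^t, for t = 8 to 15, and 16 − t assignments are then determined.
   - For t = 8, …, 15 the probabilities are 0.0078, 0.0313, 0.0703, 0.1172, 0.1611, 0.1934, 0.2095, 0.2095.
   - The mean number determined is the sum of (16 − t) times these values = 3.142.
   - P(at least 3) = 1 − 0.2095 − 0.2095 = 0.581.
2. *Random list of exactly 8 A and 8 B.* P(t determined at the end) = 2·C(15−t,7)/12870.
   - t = 1: 2 × 3432/12870 = 0.533. t = 2: 2 × 1716/12870 = 0.267.
   - P(at least 3) = 1 − 0.533 − 0.267 = 0.200. The mean is 16/9 = 1.778.
3. *Redraw all 16 flips until they are 8:8.* Each of the 12,870 balanced sequences is equally likely, so this equals the list. It takes 1/0.196 = 5.09 sequences on average.
4. *One flip per pair.* The second member of each of 8 pairs is determined, so 8.

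**How many assignments could someone tracking totals guess?** Chance alone gives 16 × 0.5 = 8.

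- Until full: only the determined assignments help, each gaining one half, so 8 + 3.142/2 = 9.57.
- List or redraw, always guessing the arm with more places left: 8 + (65536/12870 − 1)/2 = 8 + 4.092/2 = 10.05.
- Pairs: 8 × 0.5 + 8 × 1 = 12.0.

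| Rule | Mean determined of 16 | P(at least 3) | Expected correct guesses |
|---|---|---|---|
| Until one group is full | 3.14 | 0.58 | 9.57 |
| Random 8:8 list, or redraw | 1.78 | 0.20 | 10.05 |
| Flip within pairs | 8 | 1 | 12.0 |

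The list has a shorter determined tail than filling up one group, but it is slightly more guessable overall. Balance alone therefore does not solve the problem; concealment is the larger part of the remedy.

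**The case against.** The strongest reply is that nothing here is strictly contradictory. The protocol does not say the flips are independent and unrestricted, and coin-based schemes that always end 8:8 exist, including one (redrawing) that is fully random. The 0.196 then shows only that some rule is needed, not that the design fails. This is correct, and the figure is used here only in that sense. The figures by scheme likewise describe rules the protocol does not name.

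A second reply is that harm depends on facts not shown: one-at-a-time allocation, someone tracking totals, and enrolment decisions that respond to them. Read literally, the consent sentence suggests that all 16 might be enrolled first, in which case who is enrolled cannot be affected. That also stands as a possibility. But the sentence may mean only that each patient consents before taking part, and no other text fixes when allocation happens. The missing balancing rule remains under either reading.

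A third reply is that a list is no less guessable than some coin schemes, that sealed envelopes are only one form of concealment, and that an independent person to prepare them is assumed. All three points are accepted. They affect the form of the remedy, not the need for it.

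The unseen SAP does not answer the point. How patients are assigned and how assignments are concealed is normally protocol content, and this protocol has already fixed the method in its own text.

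**Conclusion.** The concern holds and should be fixed. The stated mechanism yields the stated group sizes only 19.6% of the time under fair independent flips, no rule is given for the rest, and no concealment is described. Depending on the unstated rule, the mean number of determined assignments ranges from 1.78 to 8 of 16, before counting ad hoc overrides, which would not be random.

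Confidence is high that the text is deficient. No bias is demonstrated: its size cannot be derived from the protocol, and an effect on enrolment arises only if patients are allocated one at a time without concealment.

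**What to change.** Replace the sentence under Randomization with:

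> Before the first patient, a randomly ordered list of exactly 8 A and 8 B will be generated. Assignments will be concealed in 16 sequentially numbered, opaque, sealed envelopes prepared by a department member not involved in recruitment or surgery. Each envelope will be opened only after eligibility is confirmed and the baseline ridge measurements are recorded.

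The cost is a few sentences, one list and 16 envelopes, with no extra patients or visits. It assumes that a department member outside recruitment and surgery is available; the protocol does not list staff. Another form of concealment would serve if the text names the balancing rule, who holds the sequence and when each assignment is revealed.

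One limit remains. Envelopes hide the unopened assignments but not the running totals, so anyone tracking them would still know about 1.8 of the 16 assignments in advance, on average.

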One of the most popular techniques is guided bone regeneration (GBR), which entails placing a membrane over the defect to create a secluded space into which osteogenic cells can migrate and remain undisturbed over the exposed part of the implant. Guided bone regeneration (GBR) is frequently used in combination with the installment of titanium implants. The application of a membrane to debar non-osteogenic tissues from interfering with bone regeneration is a key principle of GBR (**Elgali I et al., 2017**) (**Vijayalakshmi R et al., 2012**).

The tenting technique, which originated from the principles of guided bone regeneration, involves raising the periosteum like a tent to allow osteoblasts to migrate into the gap to start osteogenesis. The gap that is made is then filled with osteoconductive or osteoinductive materials, and in some cases, both. The migration of epithelial cells can be prevented by the application of a barrier-like collagen membrane or other component. The technique is divided into three categories that depend on the method that is used to keep the periosteum up. the first of which was the tent-pole technique. The two other modifications, cortical autogenous tenting, and screw tenting, are usually used for smaller oral defects. Studies have shown that they can all be used to augment bone effectively (**Khojasteh, A. et al., 2012**) (**Takata, T. et al., 2001**) (**Marx, R. E et al., 2002**).

To avoid shrinkage resulting from pressure after flap closure, several space maintenance modalities were used to facilitate reconstruct ridge formation such as tenting screws, titanium (Ti) meshes, and Ti-reinforced polytetrafluoroethylene (PTFE) membranes. Nonresorbable membranes have a high risk of exposure, necessitating removal in the re-entry stage. Resorbable membranes have shown better biocompatibility and support of underneath bone growth. However, their lack of stiffness can lead to decreased bone volume gain. Therefore, the tent-pole technique, which combines resorbable collagen membrane and tenting screws, represents an effective approach, offering easy manipulation and low complication rates (**Doan, Tu et al., 2020**).

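### The protocol does not fix when the assignment is disclosed, so the surgeon may know the arm while setting the crestal screw that both arms share

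*Protocol*

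**What the plan says.** **Allocation.** The protocol's Randomization section reads "All cases will be randomly allocated according to flip coin test into 2 groups each group will include 8 patients". It gives no time for the coin flip, does not say who makes it, and does not say whether or until when the result is concealed. The section stands between Pre-surgical phase and Surgical Phase, and the Group A and Group B descriptions after it already call patients candidates for one screw or two.

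**Procedure.** In Surgical Phase the flap is described without any difference by arm, followed by "Multiple cortical perforations will be performed with a 1/2 round bur". For group A, a "single titanium bone screw will be placed in a crestal position to aid in graft stability". In the two-screw arm, "double titanium bone screws will be placed, one at a crestal position and the other one will be placed 5mm apical to the first one". Then "In both groups the defect will be filled with allograft, the graft will be extended at least 10 to 12 mm in the apicocoronal direction". Membrane and closure are also common to both arms.

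**Mechanism.** Introduction and Review says that tenting "involves raising the periosteum like a tent to allow osteoblasts to migrate into the gap to start osteogenesis" and that, against shrinkage after flap closure, "several space maintenance modalities were used to facilitate reconstruct ridge formation such as tenting screws".

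**Outcome.** The comparative aim is bone gain with one screw versus two. Under Pre-surgical phase and Clinical assessment, ridge width is read by caliper to the nearest millimetre at two levels, crestal and 5 mm apical, before surgery and at 6-month reentry. CBCT is planned at both times.

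**The concern.** The treatment contrast is one added screw. Everything before it, including the crestal screw, should be done alike in both arms, and the design makes that easy to secure because the surgeon does not need the assignment until the second screw is due. The protocol does not use this opportunity and is silent on when the arm becomes known.

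The crestal screw is a space-maintaining device at the level of one of the two caliper readings. If the surgeon knows the arm when setting it, its stand-off could differ between arms without anyone intending it. A difference in crestal width gain could then reflect how the shared screw was set instead of the effect of the second screw. This is separate from whether the coin result can be predicted and from whether the 6-month reader is masked: both could be perfect and the gap would remain. It is also a matter of conduct in theatre, so a later analysis plan cannot supply a reading that was not taken.

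**Working it through.** **1. The two arms step by step (Protocol, Surgical Phase)**

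| Step | Group A | Group B |
|---|---|---|
| Flap | same | same |
| Cortical perforations | same | same |
| Crestal screw | yes | yes |
| Second screw, 5 mm apical | no | yes |
| Allograft, membrane, closure | same | same |

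The only stated difference is the fourth row. That the crestal screw goes in first in group B is suggested by the wording, which calls it the first one, but no sequence is laid down.

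**2. What is fixed in the horizontal direction.** The graft has a stated apicocoronal extent but no stated buccal thickness. No stand-off is stated for either screw, and none is to be recorded at operation.

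**3. Could the stand-off be recovered later?** CBCT is repeated at 6 months and the screws come out at reentry, also at 6 months. If the scan precedes removal, the screw and the preoperative ridge are both imaged and the stand-off might be read. The order of scan and removal is not stated.

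**4. Size, as an illustration.** The protocol has no figure to reproduce here beyond 8 + 8 = 16; it gives no SD, effect size, alpha or power. Inputs:
- n = 8 per arm (Randomization).
- Two-sided alpha 0.05: assumed.
- SD of crestal width gain 1 mm, range 0.5 to 1.5 mm: assumed.
- Arm-linked difference in mean crestal stand-off, b = 0.25, 0.5 or 1.0 mm: assumed.
- b carried fully into the 6-month crestal width, and no true effect of the second screw: assumed.

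Standard error of the difference in means: SD × √(2/8) = 0.5 × SD. Degrees of freedom: 8 + 8 − 2 = 14. Noncentrality: b / (0.5 × SD). The chance of a significant result is the two-tailed probability of that noncentral t beyond the 5% critical values. For b = 0.5 mm the noncentrality is 0.5/0.25 = 2.0 at SD 0.5, 0.5/0.5 = 1.0 at SD 1, and 0.5/0.75 = 0.67 at SD 1.5.

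| b (mm) | SD 0.5 mm | SD 1.0 mm | SD 1.5 mm |
|---|---|---|---|
| 0.25 | 15.4% | 7.5% | 6.1% |
| 0.5 | 46.1% | 15.4% | 9.5% |
| 1.0 | 96.0% | 46.1% | 23.7% |

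Each entry compares with a nominal 5%. The calculation covers the crestal reading only, not the one 5 mm apically.

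**The case against.** The other side has several fair points.

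- A reader might infer that the plan allocates before surgery. Only the section order and the word candidates point that way; the timing is unstated. This stands. The supportable statement is that disclosure is not fixed and nothing prevents the surgeon from knowing the arm.
- A reader might infer that crestal stand-off sets the limit on gain. The protocol says that tenting raises the periosteum and that tenting screws maintain space. It does not say that stand-off bounds the gain, and it gives no screw dimension. The link is a reasonable inference from the stated mechanism, no more. Nor is there a stated reason why knowing the arm would move stand-off in a particular direction.
- A reader might infer that no later check is possible. That is too strong, because the 6-month CBCT might show the screw if taken before removal.
- Full carry-over is a worst case. The introduction itself describes shrinkage under flap pressure and reduced gain with resorbable membranes.
- The protocol's probe reads to the nearest millimetre, coarser than the two smaller shifts modelled. A stand-off reading of that kind would reveal only a gross imbalance. The main protection comes from the timing of disclosure.
- Surgeons usually know the arm in surgical comparisons, and grafting, membrane placement and closure follow the second screw. Late disclosure therefore removes only part of the performance bias. It also narrows the contrast slightly, to adding a screw to one already in place.

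These points limit the claim but do not remove it. Whichever way the timing is read, the protocol leaves the arm open to the surgeon during a shared step that bears on an outcome level.

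**Conclusion.** The point holds in limited form. The protocol does not say when the assignment is disclosed, its layout suggests that it is known before surgery, and nothing withholds it while the shared crestal screw is set. Given the space-maintaining role the protocol assigns to tenting screws and the use of crestal width as an outcome, this is an avoidable route for performance bias, and no stand-off record is planned at surgery that would expose it directly.

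The figures show sensitivity, not expected bias. With 8 per arm the false-positive rate would be about 15% for a 0.5 mm shift at SD 1 mm and 7.5% for 0.25 mm. Every input except the group size is assumed. The documents do not support a reading that the trial's result will be biased. Because the remedy is cheap, the change should be made, but the trial does not fail without it.

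**What to change.** In Randomization, replace the coin flip with a concealed assignment prepared in advance, and state who opens it and when. In Surgical Phase, state that in every patient it is opened only after flap, perforations and crestal screw are complete and the crestal stand-off has been recorded, and that the second screw is then added only in group B. The choice of stand-off stays with the investigator; no value or surgical rule is proposed here. A stand-off recorded before disclosure cannot have been influenced by the arm, so it can be treated as a baseline variable.

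Costs:
- The sequence must be prepared beforehand. Little is lost: 16 independent flips give exactly 8 and 8 with probability C(16,8)/2^16 = 12,870/65,536 = 0.196, so a plain coin would seldom deliver the stated groups.
- The order of the screws in group B becomes fixed.
- One intraoperative reading is added per patient, preferably finer than the nearest millimetre.
- Grafting, membrane placement and closure remain unblinded, and the protocol should say so.

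No extra patients or visits are needed.

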**1/8/2022**

## Introduction and Review

With increasing demands of the patient regarding aesthetics and function, the need for implant supported reconstructions has substantially increased. Extensive research is being done to improve the success of implant therapy. Numerous changes in the alveolus that follow tooth loss, frequently compromises dental implant placement in a prosthetically ideal position. The natural remodelling processes of alveolar socket begin immediately after extraction and may result in up to 50 % resorption of the alveolar ridge within 3 months (**Deepika-Penmetsa, S. L et al., 2017**).

Dental implant has become an important treatment option for the treatment of partial and complete edentulism. High failure rates have been associated with implants placed in resorbed ridges with insufficient alveolar bone structure. Placement of implants in non-ideal positions as a result of bone deficiency may lead to the application of off-angle forces to the implant during function which significantly increases the force magnitude applied to the bone around the implant (**Aeh, A. et al., 2017**).

Several classification systems of alveolar ridge deformities have been proposed. Seibert introduced his widely used classification of ridge defects in 1983. In this classification, Class I defects represent buccolingual loss of tissue and normal apicocoronal ridge dimensions, Class II defects are those with apicocoronal loss of tissue and normal buccolingual ridge dimensions, while Class III defects represent a combination of both width and height deficiencies. In 1988, Cawood and Howell suggested an anatomic classification of the edentulous jaws for the preprosthetic surgery. It proposed six classes and detailed the changes that the edentulous alveolar process in anterior and posterior maxilla and mandible undergo after teeth extraction (the pattern of resorption). In 1989, Jensen proposed an implant-driven site classification by bone quality and quantity and proximity to vital structures. In 2002, Wang and Al-Shammari described a practical (therapeutically oriented) classification of alveolar ridge defects, that is, horizontal, vertical, and combination defects, proposing the edentulous ridge expansion approach (ridge-split) for the horizontal and combination defects of the alveolar Ridge. (**Cawood, J. I. et al., 1988**) (**Jensen O. 1989**) (**Wang, H. L. et al., 2002**)

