## Aim of the study

**-First aim:** Evaluate the effectiveness of screw tent technique in horizontal ridge augmentation

**-Second aim:** Compare the effect of using single screw versus double screws on obtaining maximum bone gain.

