### Inclusion criteria:

1. Selected patients of both genders are 20-55 years old.
2. Patients are systemically healthy based on questionnaire dental modification of Cornell index (**Bolender, C. L. et al., 1969**).
3. Gingival health according to the new classification system (**Caton, J. G. et al., 2018**).
4. The recipient site of the augmentation is free from any pathological conditions.
5. At least 1 tooth area with a ridge defect and planned to receive a dental implant. The site must be bordered by at least 1 tooth.
6. Class I ridge defect according to Seibert's classification.
7. Adequate interocclusal space to accommodate the available restorative components.

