### **Group B:**

8 patients indicated for lateral ridge augmentation in premolar-molar area (class I Seibert's classification) will be candidates to screw tent technique using double screws, one at a crestal position and the other one 5 mm apical to the first one.

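### Both jaws are eligible but the coin-flip allocation is not stratified by jaw, so with 16 patients jaw balance is left to chance: a modest, cheaply avoidable loss of precision

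*Protocol*

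**What the plan says.** The Patient selection section of the protocol states that "this study will be conducted on 16 patients indicated for horizontal ridge augmentation in premolar and molar area". It names no jaw. Among the inclusion criteria, the one on site asks for "At least 1 tooth area with a ridge defect and planned to receive a dental implant", again without naming a jaw, and the Group A and Group B definitions give only the premolar-molar region and the Seibert class. The Surgical Phase section shows that both jaws are foreseen: "a full thickness flap will be reflected on the lingual/palatal to expose the residual alveolar ridge". A lingual flap belongs to the mandible and a palatal flap to the maxilla.

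The allocation method is a single sentence in the Randomization section: "All cases will be randomly allocated according to flip coin test into 2 groups each group will include 8 patients". It mentions no stratification, blocking or minimisation. The comparison that depends on it is the second aim: "Compare the effect of using single screw versus double screws on obtaining maximum bone gain".

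The background notes that one cited classification "detailed the changes that the edentulous alveolar process in anterior and posterior maxilla and mandible undergo after teeth extraction". The protocol gives no figure for any difference between jaws in width gain or bone density.

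**The concern.** Jaw is known from the pre-surgical work-up, before a patient needs to be assigned, yet the stated method does not use it. Even if the two groups reach 8 each, nothing keeps the jaws evenly divided between them. If width gain or CBCT density differs between maxilla and mandible, a chance excess of one jaw in one group shifts the observed screw difference in that trial. With 8 per group, each surplus of two maxillary sites moves the unadjusted difference by a quarter of the jaw effect (2/8). At stake are the precision and readability of the second aim. Allocation is a protocol matter: an analysis plan can add a jaw term but cannot change who was assigned to what.

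**Working it through.** **Inputs from the protocol.** 16 patients, 2 groups of 8, either jaw eligible, unstratified coin flip.

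**Assumptions.** The number of maxillary patients M is not given and is varied. The jaw effect on width gain (δ) is not given; 0, 0.5, 1.0 and 1.5 mm are tried. The within-jaw SD is taken as 1 mm. Each patient is taken to contribute sites in one jaw only.

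**The plan's own figure.** 16/2 = 8 per group. A free fair coin gives exactly 8:8 with probability C(16,8)/2^16 = 12870/65536 = 19.6%, so some unstated restriction is implied. Nothing suggests that it involves jaw. The steps below grant the 8:8 split.

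**Step 1: chance of imbalance.** With a maxillary patients in group A, P(a) = C(M,a) × C(16−M, 8−a) / C(16,8).

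For M = 8:

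| Maxillary split | Probability |
|---|---|
| 4 v 4 | 4900/12870 = 38.1% |
| 5 v 3 | 6272/12870 = 48.7% |
| 6 v 2 | 1568/12870 = 12.2% |
| 7 v 1 | 128/12870 = 1.0% |
| 8 v 0 | 2/12870 = 0.016% |

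6 v 2 or worse: 1698/12870 = 13.2%. For M = 6, 5 v 1 or worse: (1440 + 90)/12870 = 11.9%. For M = 4, 4 v 0: 7.7%.

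**Step 2: effect on the unadjusted difference.** For M = 8, Var(a) = 8 × 0.5 × 0.5 × 8/15 = 1.067. The difference in maxillary proportion is (2a − 8)/8, with variance 4 × 1.067/64 = 0.0667 and SD 0.258. The same formula gives an SD of 0.25 at M = 6 and 0.22 at M = 4, so the unknown mix matters little. The within-jaw variance of the group difference is 2 × 1²/8 = 0.25. Imbalance adds δ² × 0.0667.

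| δ (mm) | SD added (mm) | Variance added | Share of total variance |
|---|---|---|---|
| 0 | 0 | 0 | 0% |
| 0.5 | 0.13 | 0.0167 | 0.0167/0.2667 = 6% |
| 1.0 | 0.26 | 0.0667 | 0.0667/0.3167 = 21% |
| 1.5 | 0.39 | 0.150 | 0.150/0.400 = 38% |

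**Step 3: what a jaw term alone would do.** For M = 8 the correlation between group and jaw is φ = (2a − 8)/8, and adjusting for jaw multiplies the variance by 1/(1 − φ²): 1.00 at 4 v 4, 1.07 at 5 v 3, 1.33 at 6 v 2 and 2.29 at 7 v 1. Weighted by Step 1: 0.381 × 1.00 + 0.487 × 1.067 + 0.122 × 1.333 + 0.010 × 2.286 ≈ 1.09. The 8 v 0 case, in which no adjusted estimate exists, is left out. So adjustment costs about 9% on average, whatever δ is, plus one degree of freedom (14 to 13). Unadjusted inflation is 0.0667/0.25 = 27% at δ = 1.0 but only 7% at δ = 0.5, so adjustment pays only once δ exceeds roughly 0.57 mm (√(0.086 × 0.25/0.0667)).

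**Step 4: stratified blocks with a jaw term.** With 8 patients per jaw and blocks of 2 or 4 in random order, each jaw splits 4:4 or, if a last block of 4 is only half used, possibly 5:3. A 6 v 2 split cannot occur. An overall 9:7 raises 1/n₁ + 1/n₂ from 0.250 to 1/9 + 1/7 = 0.254 (1.6%). With jaw in the model and the surplus in one jaw (5:3 and 4:4), the factor is 1/(15/8 + 16/8) = 0.258 (3.2%). Both are small beside the 33% that a 6 v 2 split costs an adjusted analysis.

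**The case against.** The strongest reply is that unstratified allocation is a valid design and that chance imbalance is not systematic error. This stands. A reader might infer that the design biases the screw comparison or makes false positives more likely. It does neither: over repeated randomisation the comparison is unbiased and its type I error is kept. Complete confounding has a probability of 0.016% when half the sites are maxillary.

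A reader might also infer that the protocol itself shows jaw to be prognostic. It does not. The cited classification concerns how ridges resorb after extraction, not how they respond to grafting. All sites are Seibert Class I, and gain is measured from each patient's own baseline through the same stent, so differences in starting width are largely subtracted. The 38% needs a jaw effect of 1.5 SD, for which the protocol offers no support; at zero nothing is lost.

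A third tempting reading is that 16 patients leave little room to repair an imbalance afterwards. Step 3 does not bear this out: a jaw term removes the jaw contribution for about 9% more variance on average, and for at most 7% in 87% of trials (38.1% + 48.7%). Such a term may be in an analysis plan that is not shown, so its absence from the protocol is not held against it.

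Finally, small blocks have their own weakness: the operator sees whether one or two screws are used and may guess late assignments. This is a real cost, but not clearly worse than a coin that must somehow end at 8:8.

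What remains is that a factor known in advance is left unbalanced when balancing it is nearly free.

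**Conclusion.** The point holds as a minor improvement to the design. The protocol pools both jaws and allocates without regard to jaw. The consequence is possible loss of precision and a single result that may be hard to interpret. The 13.2% chance of a 6 v 2 split or worse is exact given 8 maxillary sites and an 8:8 allocation. The 0% to 38% variance shares depend wholly on the assumed jaw effect and SD, and concern width gain analysed without adjustment; the protocol gives no basis for choosing among them, nor for a corresponding figure for density. Because adjustment alone recovers most of the loss when the jaw effect is large, stratification adds a gain of the order of 9% in variance on average, and considerably more in the roughly one trial in eight with a marked imbalance.

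**What to change.** In the Randomization section, replace the coin with concealed allocation sequences prepared in advance, one for the maxilla and one for the mandible, each in permuted blocks of randomly mixed size 2 and 4. State about 8 per group instead of exactly 8, and include jaw as a term when the groups are compared. If a patient may have sites in both jaws, say before allocation which site decides the stratum.

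No extra patients, visits or measurements are needed: two sets of envelopes replace one coin. The costs are a possible 9:7 split, one degree of freedom for the jaw term, and some predictability of late assignments within small blocks. To limit the last, block sizes should be withheld from the operator and the sequences held by someone outside the surgical team.
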